2.1 Study Rationale

Pancreatic cancer is an extremely deadly disease, with more than 95% of patients affected dying of their disease. The cancer is locally invasive and highly prone to metastasis. Although its prevalence in the USA is quite low (53,070 individuals per year), pancreatic cancer became the third leading cause of cancer-related deaths in 2016, surpassing breast cancer, and is expected to be the second cause of death by 2030 (Surveillance Epidemiology and End Results Program: Pancreas Cancer, 2016). Even though the exact etiology is unknown, 5-10% of pancreatic cancers have an inherited component, with an increased risk of developing pancreatic cancer if a first-degree relative is diagnosed with the disease. Other important risk factors associated with pancreatic cancer are smoking, long-standing diabetes mellitus, nonhereditary and chronic pancreatitis, obesity or inactivity or both, and the non-O blood group. Various genetic syndromes also pose an increased risk for developing pancreatic cancer (Kamisawa, 2016).

There are a number of types of pancreatic cancer with the predominant one being adenocarcinoma, which accounts for approximately 95% of cases. 60-70% of adenocarcinomas occur in the head of the pancreas, and 20-25% are located in the body and tail of the pancreas. The presenting signs and symptoms may be related to the location. Patients with pancreatic cancer most commonly present with abdominal pain, weight loss, asthenia, and anorexia. Obstructive jaundice is a common manifestation of tumors in the head of the pancreas (Ryan, 2014). Because the disease typically does not present with recognizable/distinctive symptoms in its early stages, when it is diagnosed, the disease is usually quite advanced with limited treatment options (Cascinu, 2010; Vaccaro, 2015). The lack of effective treatments for pancreatic cancer is evidenced by the low 5-year survival rate, which is estimated to be between 6% and 8%. Approximately half of pancreatic cancer patients present with metastatic disease for whom there are no curative therapies. These patients have a median life expectancy of less than one year, even with current treatment modalities.

Chemotherapy is the only treatment option for metastatic pancreatic cancer. National comprehensive cancer network (NCCN) treatment guidelines recommend FFX (oxaliplatin, folinic acid [leucovorin], irinotecan, bolus fluorouracil, infusional fluorouracil) or gemcitabine plus nab-paclitaxel for first line treatments for patients who are healthy enough to tolerate them and have a support system for a relatively aggressive medical therapy. In Phase III trials in patients with metastatic disease FFX was superior to gemcitabine in terms of objective tumor response, progression-free and overall survival. However, FFX is regarded as too toxic for use in elderly (Conroy, 2011; Stein, 2016) and poor performance status patients. Of note, the median age of diagnosis of pancreatic cancer is 71 years (Ryan, 2014). For patients who wish to pursue cancer-directed therapy but cannot manage such aggressive treatments, gemcitabine alone or alternate choices are recommended. In general, clinical trials are highly recommended for patients with metastatic disease. Another option for patients who cannot tolerate the toxic effects of FFX is to be treated with a modified dosing regimen of FFX, which significantly decreases the adverse side effects (neuropathy, diarrhea, neutropenia) associated with FFX.

There is a great medical need for better and more effective first-line systemic therapies that not only have less toxicity but also the potential for greater efficacy. Given the

Confidential

favorable safety and efficacy profiles of CPI-613 when administered in combination with mFFX along with the promising efficacy results achieved in trial CCCWFU57112, the further evaluation of CPI-613 in pancreatic cancer was warranted. Based on the experience in phase I study, Rafael Pharmaceuticals initiated this phase III randomized trial of standard dose FFX versus CPI-613 + mFFX in patients with metastatic adenocarcinoma of the pancreas. The goal of the trial is to provide compelling evidence of the safety and efficacy of this approach leading to a regulatory approval for CPI-613 in combination with mFFX for use in patients with metastatic adenocarcinoma of pancreas and has the potential to address serious medical unmet needs for this indication.

3. Study Design and Objectives

3.1 Study Objectives

3.1.1 z□□□□□□/ □□□□□□□□

The primary objective is:

- To evaluate Overall Survival (OS) of CPI-613® (devimistat) plus mFFX versus FFX.

3.1.2 □□□□□□□□□□/ □□□□□□□□

The main secondary objectives are:

- To evaluate Progression-Free Survival (PFS) of CPI-613® (devimistat) plus mFFX versus FFX
- To evaluate Objective Response Rate (ORR) defined as Complete Response (CR) plus Partial Response (PR) of CPI-613 plus mFFX versus FFX
- To evaluate Duration of Response (DOR) of CPI-613 plus mFFX versus FFX
- To evaluate safety of CPI-613 plus mFFX versus FFX
- To assess Pharmacokinetics (PK) of CPI-613
- To evaluate Patient-Reported Outcomes (PROs) by FACT Hepatobiliary Symptom Index (FHSI-18) for CPI-613 plus mFFX versus FFX.

3.1.3 A□□□□□□□□□□/ □□□□□□□□

Exploratory objectives are:

- To explore biomarkers using diagnostic biopsies and blood/plasma samples
- To assess PK/PD of dose/exposure-response for CPI-613 on efficacy (e.g. PFS), safety (e.g. QTc) and exploratory biomarkers.

3.2 Study Design

This is a prospective, multicenter, open label, randomized Phase III study of CPI-613 + mFFX compared to FFX in patients with metastatic (Stage IV) adenocarcinoma of the pancreas with age range of 18 to 75 years.

There will be two study arms:

- Arm 1: CPI-613 + mFFX
- Arm 2: FFX.

Confidential

Subjects will be randomized in 1:1 ratio to the experimental treatment or control, using a dynamic minimization procedure based on the methodology described by Buyse (Buyse, 2000). The minimization algorithm will use the variance method to minimize overall imbalances between the treatment arms with respect to site, performance status (0 vs. 1), and primary tumor location (head vs. body vs. tail of the pancreas).

Dosing of patients randomized in the study will continue for at least six months in responding patients with acceptable tolerance to therapy (with dose modification per protocol as needed) unless a criterion for removal from study occurs. Responding patients upon completion of at least ten cycles and after having two sequential CT scans showing stable disease (no continued decrease in lesion size) will complete two additional cycles (to complete a minimum of 12 cycles) of their assigned treatment. Following 12 cycles and all the subsequent cycles, oxaliplatin can be dropped at the discretion of the treating physician if not already omitted. Cycles will continue until one of the criteria for removal from study are reached.

z () additional information.

3.3 Sample Size Justification

A total of 500 patients will be enrolled in this trial across approximately 100 sites in North America, Europe, Asia, and Oceania. This number accounts for ineligible and unevaluable patients, as well as for dropouts.

Dropouts refer to any subject who has been randomized but withdrew for various reasons, including misdiagnosed or exclusion criteria violations.

The sample size calculation is based on the following expected benefits of the experimental treatment (CPI-613 + mFFX) over the control treatment (FFX):

- A 30% reduction in the risk of death from any cause; specifically, median OS is assumed equal to 12 months in the control arm vs. 17.14 months in the experimental arm, i.e., an OS hazard ratio equal to 0.7. For a power of 90% and a one-sided type-I error level of 0.025, 335 deaths need to be observed.
- A 30% reduction in the risk of tumor progression or death from any cause; specifically, median PFS is assumed equal to 6.4 months in the control arm vs. 9.14 months in the experimental arm, i.e., a PFS hazard ratio equal to 0.7. For a power of 90% and a one-sided type-I error level of 0.025, 330 PFS events need to be observed.

4. Data Sources

4.1 Randomization

Subjects will be randomized in a 1:1 ratio to the experimental treatment or control via an interactive web response system (IxRS), using a minimization procedure. The minimization algorithm will use the variance method to minimize overall imbalances between the treatment arms with respect to site, and the stratification factors: performance status (0 vs. 1); and, primary tumor location (head vs. body vs. tail of the pancreas). Note that region is subsumed by site, hence minimization will also tend to balance between the treatment arms with respect to geographical region.

4.2 Study Data

Study data will be collected by sites and entered into a central EDC. The EDC is maintained by IDDI. Central laboratory data will be provided by Covance.

Confidential

4.2.1 z-□□□□/ ββ

Progression-Free Survival (PFS) and Objective Response Rate (ORR) will be assessed by an independent, blinded, central review by RECIST guideline version 1.1. These data will be incorporated separately into their respective SDTM domains for further analysis.

4.3 PK

Sampling of patients for the PK analysis will occur only for the study Arm 1: CPI-613 + mFFX because the dosing level of Oxaliplatin (Eloxatin) and Irinotecan between mFFX (in Arm 1) and FFX (in Arm 2) are different. As such, PK comparison of components between mFFX and FFX is not appropriate and therefore no PK sampling for the study Arm 2: FFX.

Upon randomization through the IxRS, a patient will be designated with a code assignment for blood sampling for PK analysis of CPI-613 and its metabolites CPI-2850 and CPI-1810. Assignment will be to blood sampling for either (A) Full PK Analysis; or (B) Sparse PK Analysis. The first 10 patients will be assigned to group B. Following these 10 patients, assignment will be 24 patients to group A and the remaining 216 patients to group B. Assignment to group A will be dependent on hospital site, ability, experience, and facility to collect a more detailed blood profile over a 48-hour window.

For more details concerning the PK analysis, please refer to Section 7 of the study protocol or the separate PK Analysis Plan written and maintained by the PK vendor. As of this time, there are no planned analyses or outputs involving PK data that fall under the IDDI scope of work.

4.4 ECG

The 24 patients receiving CPI-613 plus modified FFX (i.e., Arm 1) assigned to the full PK analysis sub-study will also undergo a full ECG analysis. 12-lead ECGs will be recorded at defined intervals from 30 minutes prior to dosing of CPI-613 on cycle 1, day 1 to 6 hours after dosing on day 1. Subjects will be placed in a supine position for at least 10 minutes prior to timepoints for ECG and PK sampling. ECG recordings will be taken immediately prior to PK sample draw at each time point. ECG intervals for this full ECG analysis will be measured at a central ECG laboratory, who will be fully blinded to timepoints and subject identification.

5. General Analysis Definitions

Data will be analyzed using SAS (version 9.4 or higher).

Descriptive statistics will be tabulated as follows:

- Categorical data will be summarized in contingency tables presenting frequencies and percentages.
- Continuous data will be summarized using number of non-missing values (n), mean, standard deviation, median (25th, 75th), minimum, and maximum values.

The baseline tables will be created by treatment arm and overall. Tables containing post-randomization information will be displayed by treatment arm, unless otherwise specified.

Listings with individual values will be provided for all data presented in the tables, where noted. The listings will be presented by identifiers, such as treatment group, center, and patient number.

Confidential

One-sided tests will be used at a significance level equal to 0.025. Two-sided confidence intervals will be computed for a coverage of 0.95.

Time-to-event analyses will be performed using the Kaplan-Meier method. Subjects who have not had the event of interest at the time of the analysis will be censored at the time of the last follow up. Summary statistics will be provided by treatment arm in terms of the number of events, number of censored observations, median, and 95% confidence interval, and survival probabilities at specific time points (such as 1 year, 2 years, etc.). Survival curves will be plotted by treatment arm and compared with a log-rank test stratified by performance status and tumor location. A stratified Cox regression model will be used to estimate the hazard ratio and its 95% CI, as well as to adjust the comparison for baseline covariates.

Binary outcomes will be described by proportions by treatment arm and compared with a Cochran-Mantel-Haenszel (CMH) test stratified by performance status (0 vs. 1) and tumor location (head vs. body vs. tail of the pancreas). A logistic regression model will be used to adjust the comparison for baseline covariates.

5.1 Milestones and Planned Analyses

5.1.1 Final Analysis

The final analysis will be done with 528 patients randomized about 33 months after starting accrual, when at least 335 OS events are available. If the trial reaches statistical significance for the primary endpoint, PFS and other secondary endpoints will be tested sequentially using a type-I error level of 0.025.

5.2 Study Populations

5.2.1 Intent-to-Treat (ITT) Population

The intent-to-treat (ITT) population consists of all randomized subjects, analyzed according to the treatment arm to which they were allocated to. The ITT population will be used for all analyses of efficacy and baseline characteristics.

5.2.2 Per-Protocol (PP) Population

The per-protocol (PP) population consists of all randomized subjects who do not have any major protocol violation and received at least one dose of study treatment, analyzed according to the treatment arm to which they were randomized. The major protocol violations include inclusion or exclusion criteria deviations. The PP population will be used as a sensitivity analysis for efficacy endpoints.

5.2.3 Safety Population

The safety population consists of all randomized subjects who received at least one dose of study treatment, analyzed according to the treatment received. The safety population will be used for safety analyses.

5.3 Subgroup Definitions

Subgroup analyses will be carried out with a descriptive intent based on the subgroups described in the table at the end of this section. These analyses will repeat the OS analysis following the conventions described in section 0 using the full set of ITT patients (i.e., the subgroup analysis will take place at the same time as the final analysis). Note:

Confidential

when the particular subgroup analysis is for either of the stratification factors, only one stratification factor will be included in the `strata` statement.

A forest plot will be constructed to display the treatment effects and 95% confidence limits, number (percentage) of events, and the interaction p-value testing whether the subgroup modifies the treatment effect (e.g., the right-hand side of the `model` statement in PROC PHREG might look like `trt01p subgroup trt01p*subgroup` or `trt01p|subgroup`). The horizontal axis labels should clearly interpret the graphical result (e.g., `<-- CPI 613 + mFFX better FFX better -->`); a vertical anchor line should be drawn at 1.

Variable	Subgroups
Performance Status	Grade 0 Grade 1
Primary Tumor Location	Head of the pancreas Tail or body of the pancreas
Age	>70 55 to 70 <55
Sex	Female Male
Region	North America Europe Asia or Pacific
Race	White Black or African American Asian Native Hawaiian or Other Pacific Islander or American Indian or Alaska Native Other
Ethnicity	Hispanic or Latino Not Hispanic or Latino

5.4 Control Of Type I Error

This study has one primary endpoint of OS. The key secondary efficacy endpoint is PFS.

Testing of these two endpoints will proceed as follows in order to control the overall one-sided type I error of 0.025:

- OS will be tested at a significance level of 0.025. OS will be tested only once at the final analysis.
- PFS will be tested conditionally on the primary endpoint of OS reaching statistical significance, using the significance level of 0.025.
- If OS reaches statistical significance and PFS also reaches statistical significance, then the hierarchical testing procedure will continue to test the rest of the other secondary endpoints in the following order: ORR first, and then DOR, each at a significance level of 0.025.

5.5 Treatment Exposure

The first date of treatment will be defined as the earliest date in which a patient has a record of taking treatment with a nonzero dose; similarly, the latest date of treatment is defined to be the latest date in which a patient has a record of taking treatment with a nonzero dose.

A table will be provided summarizing treatment exposure by treatment arm in the safety population.

Confidential

5.6 Calculated Variables

- OS = 1 + date of death of any cause or censoring \square date of randomization (calculated in days then converted to months)
- PFS = 1 + date of PFS event or censoring \square date of randomization (calculated in days then converted to months)
- DOR = 1 + date of first documented PFS event or censoring \square date of initial documented response (CR or PR) (calculated in days then converted to months)
- For patients with no death date at the time of analysis, the Last alive date is defined as later of last non-missing eCRF dates
- Baseline is defined as the last non-missing assessment done before start of treatment
- Body Surface Area (m²) = ([height (cm) x weight (kg)] / 3600)^{0.5}
- Months = Days / 30.4375.

5.7 Missing Data

For the primary and key secondary efficacy analyses, imputation will be performed. Imputation rules for partial PFS dates are as follows:

- 1) If year is missing, no imputation should be done;
- 2) If only day is missing, then impute the day as the 15th of the month;
- 3) If both day and month are missing, then impute the day and month as 1st of July;
- 4) All imputed dates have to be prior to the dates of withdrawal of consent, lost to follow-up, and death.

Imputation rules for partial death dates are as follows:

- 1) When only date portion is missing and month and year are available, the death date will be imputed to the last day of that month.
- 2) When date and month portion is missing and year is available, the death date will be imputed to maximum of (30th June of year of death / last known alive date / last follow up date / maximum date from selected SDTM datasets / end of study date).

For determination of treatment emergent adverse events the following rules will be applied for all treated subjects in case of missing start date:

- If end date is before the date of first treatment administration, the start date will remain missing
- If start date is missing and end date is after or on the date of first treatment administration or the end date is missing, the start date will be imputed by the date of first treatment administration
- If start date is incomplete and end date is after or on the date of first treatment administration or the end date is missing, the start date will be imputed as follows: if the day is missing then the start date will be imputed with the first day of the month; if the day and month are missing then the start date will be imputed with minimum of (1 December of the year and the AE end date).

Confidential

6. Techniques for the Analyses

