7.3.5. Long-Term Follow-up

After the End of Treatment visit, subjects will enter long-term follow-up during which information on the subject’s survival status, disease progression and subsequent anticancer therapy will be obtained by the site every 2 months according to the protocol with a time window of +/- 7 days. Information may be collected by chart review, phone calls, clinic visits, or other means as appropriate. Long-term follow-up will continue until the subject dies, is lost to follow up, or withdraws consent.

Follow up for OS:

OS will be monitored every 2 months via telephone contact, review of hospital records, death records, social media, etc. as allowed by local laws after treatment termination (Note: During every post-study treatment telephone contact, information related to cancer treatment received will also be collected). OS and PFS will be calculated from the day of randomization.

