Supplementing this test will be a Kaplan-Meier plot showing time to progression or death from randomization, in months, by treatment arm. Underneath the plot should be a table displaying the number at risk by treatment arm at 0.5-month intervals. The plot should contain an inset with the hazard ratio, the corresponding confidence limits and p-values (both asymptotic and re-randomization test p-values).

Refer to the table below for a description of the primary and sensitivity analyses that will be performed.

No.	Stratified	Re-Randomized	Endpoint Review	Population	Additional Censoring
1. Primary	Yes	Yes	Central	ITT	2 missed visits: Y; New therapy: Y
1. Sensitivity	Yes	No	Central	ITT	2 missed visits: Y; New therapy: Y

Confidential

2. Sensitivity	Yes	No	Central	ITT	2 missed visits: N; New therapy: Y
3. Sensitivity	Yes	No	Central	PP	2 missed visits: Y; New therapy: Y
4. Sensitivity	Yes	No	Investigator	ITT	2 missed visits: Y; New therapy: Y
5. Sensitivity	Yes	No	Investigator	PP	2 missed visits: Y; New therapy: Y

The estimand corresponding to this secondary endpoint is defined by the following 5 attributes:

TREATMENT

Combination CPI-613 + mFFX compared to standard of care FFX

POPULATION

Population of patients with metastatic adenocarcinoma of the pancreas, defined through inclusion/exclusion criteria to reflect the target population. Analysis will include all randomized patients (ITT population).

VARIABLE

Progression-free survival, calculated as time from date of randomization to the date of progressive disease (assessed by an independent, blinded, central review) or death from any cause.

INTERCURRENT EVENTS (ICE) AND STRATEGIES

Death occurring before progression is observed/documented: composite strategy

Death will be considered as an event as per PFS definition.

Events leading to 2 or more consecutive missed radiographic scans before progression or death is observed: while-on-treatment strategy

radiological assessments before observed progression will be censored on the last radiological scan with documented non-progression.

Covid-19 pandemic related intercurrent events (other than those falling in the above categories): treatment policy

Treatment effect will be evaluated regardless of impact of the pandemic situation.

Treatment discontinuation: treatment policy

Any early discontinuation of treatment will be ignored (ITT principle).

Initiation of new anti-cancer therapy: hypothetical strategy

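### SAP 5.7 puts no lower limit on imputed PFS dates, so an event can precede randomisation or a clean scan, and it does not say which rule dates a death that is the PFS event

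*SAP*

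**What the plan says.** SAP 5.7 has two separate sets of rules for partial efficacy dates.

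- **PFS dates.** Day missing: "If only day is missing, then impute the day as the 15th of the month". Day and month missing: "If both day and month are missing, then impute the day and month as 1st of July". Year missing: no imputation. One constraint follows: "All imputed dates have to be prior to the dates of withdrawal of consent, lost to follow-up, and death". The SAP does not say what to do when that constraint is breached.
- **Death dates.** Day missing: "the death date will be imputed to the last day of that month". Day and month missing: "the death date will be imputed to maximum of (30th June of year of death / last known alive date", with further dates in the maximum, among them last follow-up and end of study.

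SAP 5.6 defines the time as "PFS = 1 + date of PFS event or censoring" minus the date of randomisation. For a death before documented progression, the PFS estimand in SAP 6.3.1 says: "Death will be considered as an event as per PFS definition". SAP 6.3.2 ends DOR on the date used for PFS. PFS is the key secondary endpoint, tested at one-sided 0.025 if OS is significant, followed by ORR and DOR (SAP 5.4).

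Protocol 7.3.5 describes how late information arrives: "OS will be monitored every 2 months via telephone contact, review of hospital records, death records, social media, etc". Progression status after treatment may also come from chart review or telephone.

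**The concern.** All three limits on an imputed PFS date are upper limits. Neither SAP 5.6, 5.7 and 6.3 nor the protocol sets a floor at randomisation or at the last assessment without progression. Followed literally, the rule can give a zero or negative PFS time, or a progression that predates a scan showing none. The omission looks unintended: in the same section the year-only death rule takes a maximum with last-contact dates, and adverse-event start dates are tied to first treatment.

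There is also a gap between the two rule sets. A death without progression is a PFS event, but SAP 5.7 does not say whether its date follows the PFS rules or the death rules. If the programmer has to choose, the date, and sometimes the event status, in a formally tested endpoint rests on an unrecorded decision in an open-label trial.

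**Working it through.** **Inputs.** PFS = 1 + event date - randomisation date, and months = days / 30.4375 (SAP 5.6). Imputation rules from SAP 5.7. Scans every 8 weeks +/- 7 days (Protocol 7.3.3). A gap of two or more missed scans is 126 days (SAP 6.3.1, PFS).

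**The plan's own figures.** (8 + 1) x 7 x 2 = 126 days, as stated. The 330 PFS events for 90% power at HR 0.7 and one-sided 0.025 also reproduce: the Schoenfeld formula gives 331, and power at 330 events is 0.900. Neither figure is in dispute.

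**Impossible orderings (illustrative patients).**

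| Randomised | Event known as | Imputed to | Result |
|---|---|---|---|
| 1 Sep 2020 | 2020 | 1 Jul 2020 | 1 - 62 = -61 days (-61 / 30.4375 = -2.0 months) |
| 20 Mar 2020 | Mar 2020 | 15 Mar 2020 | 1 - 5 = -4 days |
| 2 Mar 2020, clean scan 17 Aug (day 169) | 2020 | 1 Jul 2020 | day 122, which is 169 - 122 = 47 days before the clean scan |

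If the 17 August scan in the third row were the first documented response, DOR would be 1 - 47 = -46 days.

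**Which partial dates cause this.** With a +/- 7 day window, two scheduled scans are at least 56 - 14 = 42 days apart, and the first is at least 56 - 7 = 49 days after randomisation. Both exceed 31 days, so a day-missing progression at a scheduled scan never shares a month with the preceding scan or with randomisation, and the 15th causes no ordering error.

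A simulation gives the reach per partial date. Its assumptions are not in the documents: randomisation uniform over the calendar year, exponential PFS at the SAP medians, and scans exactly every 56 days.

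| Type of partial date | Before randomisation (median 6.4 / 9.14 months) | Not after last clean scan or randomisation |
|---|---|---|
| Year-only, progression at a scheduled scan | 9.7% / 7.2% | 35.0% / 34.9% |
| Day missing, progression at a scheduled scan | 0% / 0% | 0% / 0% |
| Day missing, death or unscheduled progression | 1.5% / 1.0% | 8.0% / 7.8% |

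These are shares of partial dates of each type, not of all PFS events.

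**A death that is the PFS event.** For a day-missing death, month end minus the 15th is 28 - 15 = 13 to 31 - 15 = 16 days. Randomised 2 March 2020 and died in May 2020 without progression: 15 May is day 75 and 31 May is day 91.

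The choice can change status. Take a last clean scan on 20 January 2021 and a death in May 2021. 15 May is 115 days after the scan, below 126, so an event. 31 May is 131 days after it, so censored at the scan.

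For a year-only death, the PFS rule gives 1 July. If 30 June were the maximum under the death rule, the PFS date would fall after the death date, and the SAP gives no way to resolve that.

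**The case against.** The strongest reply is that SAP 5.7 has separate lists for PFS and death dates, and that an imputed PFS date must precede death. Since a death cannot precede itself, PFS dates most naturally means progression dates. A death that is the PFS event would then take the death-rule date, and OS and PFS would agree. A reader might infer that one death necessarily receives two dates; the documents do not establish that. What stands is that the SAP never states which rule governs, and the ordering constraint suggests an answer without settling it.

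Second, other rules narrow the route. Primary PFS uses central reading of scans, which normally carry full dates. Deaths after central progression are not the PFS event. Events after a 126-day gap or after new anti-cancer therapy are censored. An End of Treatment scan is required if progression was not already documented, unless one was done within 14 days. Deaths that are serious adverse events must be reported within 24 hours of site awareness (Protocol 8.4.2), and missing data are queried to sites. All of this stands. For primary PFS, the deaths at issue are mainly those without progression or new therapy, near or within 126 days of the last scan, and with an incomplete date. Progression learned by telephone or chart review can reach only the investigator-based sensitivity analyses.

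Third, the rules do not depend on arm. A reader might infer a biased hazard ratio or an inflated type I error; neither is shown.

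**Conclusion.** The point holds as a minor defect of specification. The absence of a floor is plain from the text, and applying the SAP's own formula gives impossible times. The uncertainty over deaths is an ambiguity, not a demonstrated contradiction: a death that is the PFS event can get two dates 13 to 16 days apart, and the gap can straddle the 126-day limit.

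The size cannot be computed, because the documents do not say how many dates are partial, and it is probably small. The year-only rule is the main route to impossible orderings, and nothing suggests that year-only scan dates will be common. The simulated shares rest on the stated assumptions and describe reach within partial dates only. OS is unaffected, since it uses the death rule, and the targets of 330 PFS events and 335 deaths do not change.

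**What to change.** Amend SAP 5.7 before database lock:

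- **(a)** State that the PFS imputation rules apply to progression dates only, and that a death that is the PFS event uses the same imputed date as OS. This presupposes that the year-only death rule is itself sound; its maximum currently includes the end-of-study date and should be settled at the same time.
- **(b)** Set an imputed progression date to the latest of the 15th (or 1 July), the randomisation date, and the day after the last evaluable scan without progression. Cap it at the earliest of death, withdrawal of consent, loss to follow-up and data cut-off.
- **(c)** Replace the strict ordering against those upper dates with on or before.

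DOR then follows without further change. The cost is a few lines of SAP text and derivation code. No new data, sample size or alpha change is needed.
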